1.0 PROTOCOL SUMMARY

1.1 Protocol Synopsis

Study Title	An Open Label Phase 2 Study to Evaluate the Effects of a Local Anesthetic, Anti-inflammatory Medications and Compression Garments on RZL-012-Induced Adverse Events (RZL-012-SMF-SWMTG-P2US-001)
Phase	Phase 2
Study Drug	RZL-012
Study Objectives and Endpoints	
Primary Objective:
 
 To compare the benefits of lidocaine, methylprednisolone, Celecoxib +cetirizine or compression dressings on RZL-012-induced adverse events 
Secondary Objectives:
 
 To test the safety and tolerability profile of combining lidocaine, methylprednisolone, Celecoxib + cetirizine or compression garment with RZL-012 
Primary Endpoint: Safety and tolerability profile of combining lidocaine, methylprednisolone, Celecoxib +cetirizine or a compression garment with RZL-012
 
Exploratory Endpoints:
 
 Proportion of subjects who have at least a 1-grade improvement in the C-CAT on Day 84 versus baseline in subjects receiving RZL-012 alone or in combination with other medications. Proportion of subjects who have at least a 1-grade improvement in the S-CAT on Day 84 versus baseline in subjects receiving RZL-012 alone or in combination with other medications. Proportion of subjects who have at least a 1-grade improvement in both C-CAT and S-CAT on Day 84 versus baseline in subjects receiving RZL-012 alone or in combination with other medications. Proportion of subjects who have at least a 2-grade improvement in both C-CAT and S-CAT on Day 84 versus baseline in subjects receiving RZL-012 alone or in combination with other medications. Changes in SMF volume measured by MRI scans on Day 84 versus baseline in subjects receiving RZL-012 alone or in combination with other medications. Satisfaction in subjects receiving RZL-012 alone or in combination with other medications.
Study Design	
This is a Phase 2, open-label, 2-stage, adaptive-design study in which subjects will be randomized into one of 5 treatment groups comprised of RZL-012 with or without additional study treatments:
 
 RZL-012 alone RZL-012 and 1% lidocaine with 1:100,000 epinephrine (on Day 1) – 5ml lidocaine will be injected 10 minutes before RZL-012 treatment RZL-012 and oral methylprednisolone dose pack (8 mg (2 tablets) on Day 1 before treatment followed by 16 mg after treatment (as per Instructions for Use)). From Day 2, a daily tapering off by 4 mg until Day 6 will be administered per Rx Instructions for use.

	
4. RZL-012 and Celecoxib and cetirizine (200 mg Celecoxib BID and 10 mg cetirizine BID on Days 1, 2, 3, 4, 5 and 6)
 
5. RZL-012 + sling/pressure garment (until Day 6)
 
In the first stage of the study, 5 subjects will be randomized into each of the treatment groups. Study outcomes will be assessed up to one week thereafter to determine the need to modify additional study treatments. Subsequently up to 10 additional subjects will be randomized into each of the treatment groups for the second stage of the study.
 
For each subject, the study will consist of a screening period, baseline period in which subjects will receive a single treatment session of RZL-012 and a follow-up period. RZL-012 will be administered during a single treatment session via multiple injections into the submental area under the chin. Subjects will thereafter be monitored for safety and efficacy for at least 84 days.
 
Each subject will be treated with the same dose of RZL-012 :
 
• RZL-012 (concentration of injected solution 50 mg/mL RZL-012) of 7.5 mg/0.15 mL/injection point that results in a total dose/volume of 240±30mg mg/4.8±0.6 mL RZL-012, 
Each subject will receive additional study treatments in accordance with the treatment group to which the subject is randomized.
 
Screening Period:
 
Subjects will undergo screening within 28 days prior to being treated with RZL-012. During the screening period subjects will be assessed for study eligibility by evaluation of subjects' SMF using S-CAT , C-CAT, biochemistry blood tests, MRI, 2D photography. ECG will also be conducted during the screening visit. Following completion of study procedures (including MRI), subjects will be randomized in order for the PI to administer subjects with the Rx prescription, if appropriate (i.e., Celecoxib / cetirizine).
 
Day 1/Baseline:
 
At Baseline visit, subjects will be given with their randomized medication if appropriate. Subjects will receive a single multi-injection treatment of RZL-012 on Day 1. AEs will be recorded. Subjects will be asked about their pain levels using VAS. Additional medications/treatments, will be given according to its instructions for use.
 
Day 1-Day 84 Follow-Up Period
 
Subjects will return to the site for study visits on Days 2, 4, 7, 14, 21, 28, 56 and 84 for efficacy and safety assessments.
 
For subjects having unresolved AEs on Day 84, an unscheduled visit will be set 6-8 weeks after Day 84 to verify the resolution of the AE. On that visit, follow up of using photographs C-CAT and S-CAT will also be conducted.
 
Subjects will be advised to continue their regular diet and physical activity during the study.
 
Safety assessments include vital signs, ECG, AEs severity assessment, and treatment area evaluation. Treatment area evaluations including, but not limited to evaluation of edema, bruising, dysphasia, dysphonia, erythema, dyspigmentation, induration, numbness, pain, paresthesia, pruritus, skin ulceration and necrosis, injury to the marginal mandibular nerve, vascular and nerve injury and tissue damage to nearby vulnerable anatomic structures. Specifically, degree of swelling severity will be assessed as a function of time and in each visit Subjects will be asked about their pain levels using VAS. Pain at injection site will not

--	--

	be recorded as an AE but the information regarding pain will be obtained from the VAS scores completed by the subject. Concomitant medications will be recorded.
Sample Size	Up to 75 subjects (5 in each treatment group in stage 1 of the study and up to 10 subjects in each treatment group in stage 2 of the study).
Study Population	Adult volunteers age 18 to 65 years who have consented to participate in this study.
Main Inclusion Criteria	
For a subject to be eligible for this study, he or she must meet all of the following criteria:
 
 1. Is a male or female subject between the ages of 18 and 65 years, inclusive. 2. Has body mass index (BMI) between >22 kg/m² and <40 kg/m². 3. Has SMF bulge that is contiguous and fits to 32±4 injections sites according to a grid with 1 centimeter (cm) distance between injection points. 4. Has grade 3 to 4 of SMF as rated by both the C-CAT and S-CAT. 5. Has stable weight, with no fluctuation of >5 kg in the past 12 months. 6. If female, is not pregnant or breastfeeding based on the following: 
 a. agree to the use of highly effective contraceptive methods for at least 2 weeks before baseline until 4 weeks after the last day of study drug and a negative serum pregnancy test (β-hCG) at screening and negative urine pregnancy test at baseline; or b. is abstaining c. is of nonchildbearing potential defined as clinically infertile as the result of surgical sterilization (hysterectomy, bilateral tubal ligation, and/or bilateral oophorectomy); or d. is confirmed postmenopausal status (defined as either having amenorrhea for ≥ 12 consecutive months without another cause or documented serum follicle-stimulating hormone (FSH) level > 40 mIU/mL or another documented medical condition (e.g., was born without a uterus)) 
NOTE: The following are considered highly effective contraceptive methods: hormonal oral contraceptives, injectables, and patches; intrauterine devices; double-barrier methods (synthetic condom, diaphragm, or cervical cap used with spermicidal foam, cream, or gel); and male partner sterilization.
 7. If male (with or without vasectomy), agree to the use of highly effective contraceptive methods as listed above in criteria 7 as well as to use a barrier method, e.g. condom , from study check-in until 7 days after drug injection. 8. Is willing to avoid strenuous exercise for seven (7) days post treatment. 9. Is able to adhere to the visit schedule and protocol requirements and be available to complete the study. 10. Is willing and able to sign an Institutional Review Board (IRB) approved informed consent form (ICF) indicating that they are aware of the investigational nature of the study.
Main Exclusion Criteria	
Subjects must NOT meet any of the following Exclusion criteria to be eligible for enrollment:
 
 1. Is unable to tolerate subcutaneous injections. 2. Has any systemic disease including but not limited to gastritis or ulcers, renal dysfunction, hypertension, liver disease, glaucoma, diabetes and/or cardiovascular disease, , regardless of whether the condition is controlled with medication. 3. Has any contraindications to oral corticosteroids (methylprednisolon), NSAIDs (e.g., Celecoxib) or non-sedative antihistamines (e.g. cetirizine)

	
 4. Has skin laxity (i.e., elastosis, skin crepiness, skin redundancy, skin draping, vertical and/or horizontal skin bands and folds, blunting of cervical mental angle, loss of opposition of skin to underlying neck structures due to skin laxity) that could obscure the evaluation and treatment of SMF. 5. Has any scars, unshaven hair, tattoos, facial hair or jewelry on or near the proposed treatment area. 6. Has presence of structures or confounding factors that may interfere with assessing SMF such as but not limited to enlarged submandibular salivary and/or parotid glands, micrognathia, chin implant, soft tissue volume augmentation of chin and/or jawline, pronounced platysmal bands and deep necklace lines or presence of facial jowls that could obscure the evaluation of SMF. 7. Has a fat bulge under the chin that is too large to be adequately treated by 32±4 contiguous injections on a 1cm grid . 8. Has a fat bulge under the chin that is of an insufficient volume to allow 32±4 injections within a contiguous 1 cm grid. 9. Has significant history or current evidence of a medical, psychological or other disorder that, in the Investigator’s opinion, would preclude enrollment in the study. 10. Has an active bacterial, fungal, or viral infection in the proposed treatment area. 11. Has a pre-existing skin condition in the submental region that, at the Investigator’s discretion, may confound evaluation or analysis. 12. Has previously had treatments or surgery in the submentum, such as but not limited to, focused ultrasound, radiofrequency, cryolipolysis, liposuction, sodium deoxycholate, or neck lift. 13. Has pre-existing neurological or gastrointestinal condition leading to dysphagia, dysphonia, or facial nerve palsy. 14. Has Dercum’s Disease. 15. Has allergic reactions to injectables 16. Has allergic reactions to cetirizine or Celecoxib. 17. Has any pre-existing medical condition other than increased SMF that, at the Investigator’s discretion, may result in increased submental fullness, such as but not limited to, thyroid enlargement, goiter, cervical lymphadenopathy, etc. 18. Has a planned fat reduction procedure of any variety to the submental region for the duration of the study. 19. Has medication or a history of coagulopathy. 20. Has a history or family history of venous thrombotic disease. 21. Has been treated chronically at least three (3) months prior to study entry with systemic steroids or immunosuppressive drugs. 22. Has been treated chronically at least one (1) week prior to study entry with non-steroidal anti-inflammatory drugs (NSAIDs) 23. Has used anticoagulation therapies that may increase bleeding or bruising (i.e., aspirin, ibuprofen/Celecoxib, warfarin, vitamins, and herbal preparations) for seven (7) days prior to treatment. 24. Has had treatment with botulinum toxin injections in the neck or chin area within nine (9) months prior to screening. 25. Current participation or participation within three (3) months prior to the start of this study in a drug or other investigational research study. 26. Claustrophobia or MRI incompatible device or implant. 												

Dosage and Administration of Study Drug
	
Subjects will receive study treatments in accordance with the treatment group to which the subject is randomized:
 
  
 	Group 1	Group 2	Group 3	Group 4	Group 5	
   
 Day 1	RZL-012	RZL-012 + 1% lidocaine with	RZL-012 + methylpredn	RZL-012 +	RZL-012 +	
  
		Group 1	Group 2	Group 3	Group 4	Group 5	Day 1	RZL-012	RZL-012 + 1% lidocaine with	RZL-012 + methylpredn	RZL-012 +	RZL-012 +
	Group 1	Group 2	Group 3	Group 4	Group 5								
Day 1	RZL-012	RZL-012 + 1% lidocaine with	RZL-012 + methylpredn	RZL-012 +	RZL-012 +								

		1:100,000 epinephrine (10 minutes prior to RZL-012)	isolone dose pack (the first dose of 2 tablets (8mg) is administered 1-2 hours prior to RZL-012) A total of 24 mg (16 mg after RZL-012, as per IFUs)	200 mg Celecoxib BID and 10 mg cetirizine BID (the 1 st dose is administered 1-2 hours prior to RZL-012).	pressure garment
Day 2			20 mg methylprednisolone	200 mg Celecoxib BID and 10 mg cetirizine BID	pressure garment
Day 3			16 mg methylprednisolone	200 mg Celecoxib BID and 10 mg cetirizine BID	pressure garment
Day 4			12 mg methylprednisolone	200 mg Celecoxib BID and 10 mg Zyrtec BID	pressure garment
Day 5			8 mg methylprednisolone	200 mg Celecoxib BID and 10 mg cetirizine BID	pressure garment
Day 6			4 mg methylprednisolone	200 mg Celecoxib BID and 10 mg cetirizine BID	pressure garment

BID = twice daily,

RZL-012 will be administered via multiple injections (32±4) for a total dose of 240±30 mg. Each injection point will be dosed with 7.5 mg RZL-012 in a volume of 0.15 mL/injection site. The total injection volume for all groups will be 4.8 mL±0.6.

	
Subjects will be injected with RZL-012 perpendicularly (90°) to the skin. An ice pack will be placed on the injected area for pain relief immediately after injection. Subjects will remain seated in the injection position for an additional 10 minutes after dosing.
 
The injection pattern will be based on a submental area shaped grid in which the distance between rows and columns will be 1 cm, as seen in the figure below. The Investigator will choose 32±4 sequential points on the grid that will mark the injected area according to SMF fullness and convexity. The treatment area boundary: superiorly by a line 1 cm inferior to the mandibular margin, laterally by the sternocleidomastoid muscles, and inferiorly by the hyoid bone.
 

Safety Analysis
	
AEs will be collected and reviewed to evaluate the safety and tolerability of RZL-012. AE collection will begin after dosing and will end at on Day 84. For subjects having unresolved AEs on Day 84, an unscheduled visit will be set 6-8 weeks after Day 84 to verify the resolution of the AE.
 
Other safety measures will include vital sign measurements, laboratory parameters, ECG, and treatment area evaluation including, but not limited to evaluation of edema, bruising, dysphasia, dysphonia, erythema, dyspigmentation, induration, numbness, pain, paresthesia, , pruritus, skin ulceration and necrosis, injury to the marginal mandibular nerve, vascular and nerve injury and tissue damage to nearby vulnerable anatomic structures. Specifically, swelling severity will be assessed in each visit, subjects will be asked about their pain levels. Pain at injection site will not be recorded as an AE but the information regarding pain will be obtained from the VAS scores completed by the subject. AEs related to nerve injury will be AEs of special interest. Concomitant medications will be recorded.


Statistical Analysis
	
All measured variables and derived parameters will be listed individually and, if appropriate, tabulated by descriptive statistics.
 
For categorical variables, summary tables will be provided giving sample size, absolute and relative frequency, and 95% confidence interval (CI) for proportions by study arm.
 
For continuous variables, summary tables will be provided giving sample size, arithmetic mean, standard deviation, coefficient of variations (CV%), median, minimum and maximum, and 95% CI for means of variables by study arm.
 
Primary endpoint and exploratory endpoints will be analyzed in descriptive manner.
 
The data will be analyzed using the SAS version 9.4 (SAS Institute, Cary North Carolina).

Study Duration
	
It is planned that each subject will participate in the study for 4 months, which comprises a screening period, baseline/treatment period, and follow up period.

Study Centers
	
6 clinical centers

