2.0 INTRODUCTION

1.1. Study Rationale

The recent clinical study (RZL-012-SMF-P2b-US-001) was a double-blind, randomized, three-arm, placebo-controlled Phase 2b study that tested the efficacy and safety of RZL-012 injections into the submental fat in 151 subjects. Single administration of high dose RZL-012 (50mg/ml) resulted in a clinically meaningful reduction in submental fat. The efficacy of the RZL-012 high dose was higher than that of the low dose and of the placebo. Local injection-site reactions were the most commonly reported AEs with injection-site pain, nodules induration and edema being clearly RZL-012 related. Injection-site severe swelling in the submental area was shown to be associated with additional AEs such as dysphagia, dysphonia, and dyspnea.

This clinical trial will assess ways to reduce AEs related to swelling and pain.

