5.2 Exclusion Criteria

Subjects must **NOT** meet any of the following exclusion criteria to be eligible for enrollment:

1. Is unable to tolerate subcutaneous injections
2. Has any systemic disease including but not limited to gastritis or ulcers, renal dysfunction, hypertension, liver disease, glaucoma, diabetes and/or cardiovascular disease, regardless of whether the condition is controlled with medication.
3. Has any contraindications to oral corticosteroids (prednisone), NSAIDs (e.g., Celecoxib) or non-sedative antihistamines (e.g. cetirizine)
4. Has skin laxity (i.e., elastosis, skin crepiness, skin redundancy, skin draping, vertical and/or horizontal skin bands and folds, blunting of cervical mental angle, loss of opposition of skin to underlying neck structures due to skin laxity) that could obscure the evaluation and treatment of SMF.
5. Has any scars, unshaven hair, tattoos, facial hair or jewelry on or near the proposed treatment area.
6. Has presence of structures or confounding factors that may interfere with assessing SMF such as but not limited to enlarged submandibular salivary and/or parotid glands, micrognathia, chin implant, soft tissue volume augmentation of chin and/or jawline, pronounced platysmal bands and deep necklace lines or presence of facial jowls that could obscure the evaluation of SMF.
7. Has a fat bulge under the chin that is too large to be adequately treated by 32 ± 4 contiguous injections on a 1cm grid .
8. Has a fat bulge under the chin that is of an insufficient volume to allow 32 ± 4 injections within a contiguous 1 cm grid.
9. Has significant history or current evidence of a medical, psychological or other disorder that, in the Investigator's opinion, would preclude enrollment in the study.
10. Has an active bacterial, fungal, or viral infection in the proposed treatment area.
11. Has a pre-existing skin condition in the submental region that, at the Investigator's discretion, may confound evaluation or analysis.
12. Has previously had treatments or surgery in the submentum, such as but not limited to, focused ultrasound, radiofrequency, cryolipolysis, liposuction, sodium deoxycholate, or neck lift.
13. Has pre-existing neurological or gastrointestinal condition leading to dysphagia, dysphonia, or facial nerve palsy.
14. Has Dercum's Disease.
15. Has allergic reactions to injectables
16. Has allergic reactions to cetirizine or Celecoxib.

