9.4 Safety

Safety data will be summarized by dose group and based on their initial dose level or treatment group (i.e., if a dose reduction occurs, they will be considered in their initial group). Descriptive statistics will be provided for actual values and change from baseline values for vital signs, blood parameters, ECG.

AE assessment and treatment area evaluation including, but not limited to evaluation of edema, pain, bruising, erythema, induration, numbness, paresthesia, tenderness, and pruritus. Pain in the injection site will be assessed by Visual Analog Scale (VAS) in each of the visits. Injection site pain will not be recorded as an AE.

The incidence and severity of AEs reported during the study and their relationship to study drug will be tabulated. AEs will be coded using MedDRA™ and will be presented by body system.

AEs related to nerve damage such as: paralysis, mandibular neuropathy, facial palsy will be AEs with special interest, i.e., the PI will write a detailed narrative on these specific AEs.

AE data will be listed individually and summarized by SOC and by PT within a system organ class.

Skin irritancy AEs related to the injection procedure will be evaluated for frequency, severity and duration by treatment group.

Laboratory tests and ECG results will be summarized in appropriate table.

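### The treatment-area lists misprint dysphagia, omit dyspnea, and in Section 9.4 name none of the three events tied to severe swelling, so uniform capture of these events is not assured

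*Combined protocol and SAP*

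**What the plan says.** The Study Rationale (Section 2.0) states that severe injection-site swelling in the Phase 2b study "was shown to be associated with additional AEs such as dysphagia, dysphonia, and dyspnea". It then gives the purpose of the present trial: "This clinical trial will assess ways to reduce AEs related to swelling and pain".

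The treatment-area evaluation is described in three places. Under Study Design in the synopsis it is "evaluation of edema, bruising, dysphasia, dysphonia, erythema, dyspigmentation, induration" and further items. Under Safety Analysis in the synopsis it begins in the same way: "evaluation of edema, bruising, dysphasia, dysphonia, erythema, dyspigmentation, induration, numbness, pain, paresthesia". Section 9.4 gives a shorter list: "evaluation of edema, pain, bruising, erythema, induration, numbness, paresthesia, tenderness, and pruritus". All three are introduced as non-exhaustive.

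Exclusion criterion 13 uses the other spelling: "Has pre-existing neurological or gastrointestinal condition leading to dysphagia, dysphonia, or facial nerve palsy".

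Adverse events are the subject of the primary objective, and safety is the primary endpoint (Sections 3.1.1 and 3.2.1). Special-interest status is given only to events related to nerve injury (synopsis, Safety Analysis; Section 9.4).

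**The concern.** The trial compares four add-on measures with RZL-012 alone, and swelling and its consequences are a main target. Trouble with swallowing, voice or breathing is what the sponsor's own earlier study linked to severe swelling. One would expect the plan to name these events in the same words wherever it says what is to be evaluated. Instead, a site that follows the synopsis literally is told to look for a language disorder, is not reminded of dyspnea, and finds none of the three in the statistical section.

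What is at stake is even ascertainment across arms. Subjects and investigators know the assignment (Section 4.2). Where an event is not asked about in a fixed way, the chance that it is recorded can depend on how hard someone looks or how readily someone complains, and in an open-label comparison either can differ by arm.

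**Working it through.** No figure in the plan bears on this, so the check is a comparison of the texts.

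**Step 1: the three events against the three lists.**

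| Event in the rationale | Synopsis, Study Design | Synopsis, Safety Analysis | Section 9.4 |
|---|---|---|---|
| Dysphagia | printed as *dysphasia* | printed as *dysphasia* | not named |
| Dysphonia | named | named | not named |
| Dyspnea | not named | not named | not named |
| Correctly named | 1 of 3 | 1 of 3 | 0 of 3 |

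Over the three lists, 1 + 1 + 0 = 2 of 9 entries are correct. Edema and pain appear in all three lists.

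**Step 2: is *dysphasia* a slip?** The rationale and exclusion criterion 13 both pair *dysphagia* with dysphonia. The synopsis lists put *dysphasia* in the same position, directly before dysphonia. No language disorder is mentioned anywhere else as an effect of the drug. The misprint is evident from the document itself.

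**Step 3: is there another definition of the evaluation?** The Schedule of Activities (Section 1.2) has no row for it, only a combined row for adverse events and the VAS. None of the assessment subsections in Section 8 describes it. The three lists are therefore the only specification a site or an eCRF builder has in this document.

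**Step 4: does general adverse-event collection fill the gap?** Partly.
- Section 8.15.1 counts any unfavorable sign or symptom as an adverse event. Section 1.2 schedules collection on Day 1 and Days 2, 4, 7, 14, 21, 28, 56 and 84, which is nine visits. Section 9.4 tabulates adverse events by system organ class and preferred term. The three events fall within this.
- Section 8.15.1 also prefers, where possible, that the diagnosis be entered in place of its symptoms. A subject with severe swelling who has trouble swallowing or breathing may then appear only under swelling or edema. A table by preferred term cannot recover a term that was never entered.
- The special-interest category, the other route to closer recording, covers nerve injury only.

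**Step 5: how much one subject weighs.** Stage 1 has 5 subjects per arm, and its outcomes inform whether the add-on treatments are modified (Section 4.1). Stage 2 adds up to 10, giving up to 5 + 10 = 15 per arm. One unrecorded subject lowers an arm's observed rate by 1/5 = 20 percentage points in stage 1, or 1/15 = 6.7 points at full size. This shows the sensitivity of small arms. It does not estimate how many events would be missed.

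**The case against.** The strongest reply is that nothing is excluded. Every list is open-ended, the definition of an adverse event takes in all three symptoms, collection runs at every visit from Day 1, and all recorded events are tabulated. Section 9.4 also leaves out dyspigmentation, ulceration and necrosis, so it reads as an abbreviation and not as a decision to drop these events. Dyspnea is not a local finding, so its absence from a list about the treatment area is understandable, and respiratory rate is measured at every visit (Section 8.12). Swelling severity and pain, the stated targets, are assessed throughout.

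Most of this stands, and it rules out three stronger readings that a reader might infer.
- *That the events will not be asked about.* The documents show narrative lists and no form, so how subjects are questioned cannot be determined.
- *That swallowing trouble will be coded to the wrong MedDRA term.* Under Section 8.15.1, preferred terms are assigned to what is entered on the CRF. The synopsis misprint has no effect on coding unless an investigator copies it.
- *That a given share of events will be lost.* The documents give neither event rates nor reporting fractions, so no such figure can be supported.

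What the reply does not answer is the preference for diagnoses over symptoms. Being covered by the definition of an adverse event does not ensure that a symptom is recorded separately when its cause is also recorded. Respiratory rate is only a partial stand-in for reported breathlessness.

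**Conclusion.** The point holds as one of specification and consistency. The misprint occurs twice and should be corrected in any case. Dyspnea is missing from both synopsis lists, and all three events from Section 9.4. The events remain reportable and will be tabulated if entered, but the plan does not ensure that they are sought and recorded in the same way in every arm.

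The matter is moderate in weight. It touches the primary safety comparison, but it invalidates no analysis, and the analyses are descriptive in any case. The size of any loss in ascertainment is unknown. The conclusion rests on two assumptions: that no eCRF or site manual outside these documents already asks about the three events separately, and that the part of the introduction I could not see, between the Phase 2b efficacy results and the liver-enzyme paragraph, gives no assessment instruction.

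**What to change.** 1. In both synopsis lists, replace *dysphasia* with *dysphagia* and add dyspnea.
2. In Section 9.4, add dysphagia, dysphonia and dyspnea to the list.
3. Record each of the three as its own yes/no item, with severity, at the existing adverse-event visits, with the question covering the time since the previous visit. State in Section 8.15.1 that they are entered even when swelling or edema is also recorded.
4. Tabulate the incidence and severity of the three events by arm, beside swelling severity.

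The cost is three items at each of nine visits, or 3 × 9 = 27 entries per subject and 27 × 75 = 2,025 at full enrollment. No visit, procedure or subject is added. There are two limits. Solicited rates will run higher than volunteered ones, so they will not be directly comparable with any earlier rates collected as volunteered reports. Fixed questions also even out the asking but not the answers, which subjects still give knowing their treatment.
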